5.0 Procedures Involved

5.1 Study Design:

We will use a cluster randomized trial design. We will recruit 12 community sites (“clusters”) in low-income neighborhoods and/or adjacent to low-income housing residences with 22 participants per site. To enhance feasibility, we will conduct the study in three waves, with 4 community sites in wave 1, 4 community sites in wave

2, and 4 community sites in wave 3. For each wave, following participant baseline data collection that will occur at the same time across the sites of the wave, we will randomize sites to receive the full-service market intervention or serve as a waitlist control. Sites randomized to receive the market will begin weekly service immediately following 2 months of strategic community engagement led by the community partner at The Food Group with the Mobile Market (see section 4 above). After 6 months of market operation, follow-up data collection will occur for outcome measurement followed by qualitative interviews with a subset of intervention participants (high and low adopters). The RE-AIM (reach, effectiveness, adoption, implementation, maintenance) framework guides our evaluation.⁸⁷⁻⁸⁹ This process will be repeated for Wave 2 and 3 sites. Intervention sites will continue to receive the market during and after the follow-up data collection period. The waitlist sites for Waves 1, 2, and 3 will receive the intervention following final data collection for the wave.

5.2 Study Procedures:

Recruitment of sites: See details in IRB protocol section 9.0 and 12.

Recruitment of individuals from sites recruited for the trial. See details in IRB protocol section 9.0 and 12. See also “eligibility screening script” document.

Baseline Data collection: The consent forms will be mailed to interested and eligible participants in advance of the baseline data collection visit. The process of informed consent will take place at baseline data visits in a private and confidential space [using a privacy screen if needed]. Data collection will occur at baseline (after site recruitment but before site randomization is known to sites, participants, research staff, the PI, and non-statistician University co-investigators) and again at follow-up (after 6 months of mobile market service at sites randomized to the intervention) for all sites. Data collection will occur simultaneously at intervention and waitlist sites to minimize the threat of temporal trends (e.g., changes in community, policy, or economic climate). Data collection will occur onsite or in nearby community locations and over the telephone. Mobile market purchasing data collection will occur during and after the intervention through the end of data collection for participants at sites randomized to receive the mobile market first. Implementation process data collection will occur throughout the trial and participant process data collection will occur after the 6 month implementation of the mobile market intervention. If sites do not have adequate privacy, we will create a private space with privacy screens. The surveys will be completed by participants using a Health Sciences registered iPad using a secure web-based REDCap survey. In case of technical failure, paper-pen back-up surveys will be available. If this is needed, paper-pen surveys will be entered into a secure REDCap database¹¹⁸ by two study staff and verified for accuracy. Diet recall data will be entered in Nutrition Data System for Research (NDSR) software by trained staff. The data will be stored on

SOCIAL PROTOCOL (HRP-580)

PROTOCOL TITLE: Mobile Food Market Cluster Randomized Trial

VERSION DATE: 1/5/2023

secure University laptops and backed-up to secure BOX data servers. Paper files will be stored in secured, locked file cabinets. See the table below for a broad overview of timeline of data collection and measurement. Details for each of the measures is provided below the table.

	Screening	Baseline	6 month intervention	Follow-up data collection	Qualitative interviews
Eligibility and study interest	x				
Informed Consent		x			
Diet Quality (measured with 3 dietary recalls - one in person, and 2 in the next three weeks by phone)		x		x	
Food security		x		x	
Fruit & Vegetable form completion for 4 weeks		x		x	
Personal, social, behavioral, and environmental factors survey		x		x	
Demographics		x			
Randomization**		x			
Adverse Events		x	x	x	
Mobile market shopping purchases (intervention participants only)			x		
Quantitative measures of mobile market factors that may influence shopping adoption (intervention participants only)				x	
Qualitative interviews with a subset of intervention participants (high & low adopters)					x
Process measures			x	x	

** Randomization occurs after site recruitment for the Wave is complete (about 2 months prior to the end of data collection for the wave. Sites (and the participants attached to those sites) will be randomized to receive mobile market service or to the waitlist (to receive mobile market service after data collection for the wave is complete). After randomization, the study statistician will be unblinded to site names by being provided access to the key that matches sites with their assigned numbers. This will inform him which sites were randomized to the intervention and waitlist control. The study statistician will inform the mobile market co-investigator of the sites randomized to the intervention approximately 2 months prior to the end of data collection to allow time for the mobile market to plan for market routes and schedules. Participants, site locations, the PI, and other UMN trial investigators and staff will be blinded to (i.e., not be informed of) site randomization results until after baseline data is collected. The mobile market co-investigator will explicitly instruct the market drivers (who will help plan the routes with the new stops for the trial sites) that the knowledge of sites is strictly confidential until after baseline data collection is complete and contact between mobile market staff (aside from the Mobile Market co-investigator) and research team, PI, and University staff will not occur during this time to reduce any potential for unintentional disclosure.

Diet quality will be measured through 24-hour dietary recall interviews. Trained staff certified in collecting diet recalls using Nutrition Data System for Research (NDSR) will collect three 24-hour recall interviews (2 weekdays, 1 weekend day)

SOCIAL PROTOCOL (HRP-580)

PROTOCOL TITLE: Mobile Food Market Cluster Randomized Trial

VERSION DATE: 1/5/2023

from each participant at both measurement periods (baseline, follow-up). At each measurement, the first recall will be conducted in-person during data collection visits; the second two recalls will be by phone. NDSR,⁹⁴ a diet analysis software developed and maintained by the University of Minnesota Nutrition Coordinating Center (led by co-investigator [name]) will be used to collect recalls. The multiple-pass interview technique will be used to prompt for complete recalls and descriptions.⁹⁵ A Food Amounts Booklet adapted from Van Horn et al.⁹⁶ will be provided to participants for use in estimating food and beverage amounts (attached).

To measure diet quality, Healthy Eating Index-2015 (HEI-2015) total and components scores will be calculated from the recall data. The HEI-2015 is a scoring system to measure adherence to the 2015-2020 Dietary Guidelines for Americans (2015-2020 DGA).^{69,70} The HEI-2015 total score is the sum of 13 subcomponents that measure adequacy (Total Fruits, Whole Fruits, Total Vegetables, Greens and Beans, Whole Grains, Dairy Products, Total Protein Foods, Seafood and Plant Proteins, and Unsaturated:Saturated fats) and moderation (Refined Grains, Sodium, Added Sugars, and Saturated Fats). All subcomponents are scored from 0-5 or 0-10 based on intake between minimum and maximum standards. Moderation components are reverse scored so higher scores reflect lower intake. A higher HEI-2015 score (out of 100) represents greater consistency with the 2015-2020 DGA. Additional diet outcomes from recall data include mean daily intake of: energy, fruits and vegetables (servings/day), added sugar (% calories from added sugar) and sodium (mgs/day)..^{69,70} See dietary recall protocol.

Food insecurity. Food insecurity in the past 6 months will be measured with the gold-standard, 18-item food security screening module of the USDA, which will allow for assessment of both binary food insecurity (yes, food insecure; no, food secure) and level of food security (very low, low, marginal, and high food security).⁹¹ We will assess for change in prevalence of food insecurity and level of food security from baseline to follow-up (e.g., change in % very low food security from baseline to follow-up), as assessed in other community-based food intervention studies aiming to improve food security.^{97,98} We will also use newly developed and validated measures to assess ***nutrition insecurity*** in the past 6 months, which helps us understand fuller contexts around choices people may make when money is tight (e.g., compromise nutrition for a full stomach).¹³⁷ These measures will be collected via REDCap, which makes the skip patterns invisible and easy for participants.

Fruit & Vegetable purchasing outcomes: Participants will record the fruits and vegetables that they buy along with the date and place of purchase using forms in provided booklets, and mail these booklets to the researchers in prepaid addressed envelopes, which will be used to measure:

Average weekly servings of fruits & vegetables. The purchase quantity (volume, weight, quantity) of fruits and vegetables from the forms will be entered into NDSR. Using these data, NDSR will calculate the edible

servings for each item. This process accounts for and eliminates the inedible portions of foods (e.g., peels, pits). The edible servings purchased will be summed and averaged to obtain the average servings of fruits and vegetables purchased weekly across all purchase locations. See Fruit & Vegetable Purchasing data collection protocol and Fruit & Vegetable purchasing booklets for participants attachments.

Descriptive purchasing variables measured with data from the fruit & vegetable forms. Total number of trips and store types visited will be measured using the data from the fruit & vegetable forms. See the Fruit & Vegetable Purchasing Data Collection Protocol and Fruit & Vegetable purchasing booklets for participants attachments.

Shopping adoption. Intervention participant shopping adoption will be measured in 2 ways: (A) average monthly dollars spent and frequency of shopping at the mobile market during the implementation period and 3 months post-implementation as measured by purchases with customer loyalty cards (see Mobile Market purchasing data protocol attachment); and (B) self-reported average frequency of mobile market shopping each month (see process survey attachment).

Quantitative measures of personal, social, behavioral, and environmental factors. At baseline and follow-up, surveys with validated psychosocial measures will be used to measure factors that may influence mobile market adoption. These factors include: Neighborhood Healthy Food Availability (4 item scale; $\alpha=0.89$);⁹⁹ Social Connectedness (8 item scale, $\alpha=0.92$);¹⁰² Health-related quality of life (4-items);¹⁰³⁻¹⁰⁷ Self-efficacy of Healthy Cooking (4 item scale, $\alpha=0.85$);¹⁰⁹ Self-efficacy for eating and cooking fruits and vegetables (4 item scale, $\alpha=0.90$);¹⁰⁸ and Everyday Discrimination Scale (6 item scale $\alpha=0.77$ + 2 follow-up items).¹³⁹⁻¹⁴⁰ Item responses will be coded and summed so a higher scale score indicates a higher trait (e.g., higher access to affordable quality foods). See psychosocial survey attachment.

Other data to be collected

Participant information, demographic information, and potential confounding variables. Participants will self-report by survey age; sex; income level (<10,000, 10,000 to <15,000, etc); education level (some high school, graduate equivalent degree [GED], some college, etc.); receipt of SNAP, WIC, free or reduced price school lunches, other food programs and medical assistance; household size; ethnicity; race (American Indian or Alaskan Native, Asian, Black or African American, Native Hawaiian and Other Pacific Islander, White; selecting all that apply); and diet/weight related health conditions. See attached surveys (Note: Most of these questions are in the demographics survey; the health related questions are in the psychosocial survey and the household size questions are in the food security survey.)

Process data. Aligned with the RE-AIM framework,¹¹²⁻¹¹⁴ we will collect process measures during and immediately following the intervention to assess

SOCIAL PROTOCOL (HRP-580)

PROTOCOL TITLE: Mobile Food Market Cluster Randomized Trial

VERSION DATE: 1/5/2023

reach, adoption, implementation, and maintenance. See table below.

Process Measures (RE-AIM alignment)	Collection Method	Data collected	Who / When	Analysis
Site mobile market operation implementation fidelity (I)	Assessments for deviations in scheduled operation (e.g., related to weather, traffic, repairs), stocking practices, and pricing.	
 Documented deviations (see Fidelity Bus Operations Data Collection Protocol) 	Regularly monitored by study staff during the implementation period	Descriptive
Site sales: use and reach by site (R, A)	The cloud-based, electronic, point-of-sale, cash register records all sales transactions.	
 Date, time, site of sale, payment type, and foods items/categories sold for all transactions (data to be collected are not identifiable or linked to participants – rather this data will be used to describe sales at intervention sites and make comparisons to waitlist and other non-research sites) 	Downloaded monthly by study staff during the implementation period	Descriptive. Total sales and sales by food category for intervention sites
Contamination and dose— self-reported (R, A)	Survey will include questions to assess market dose and contamination exposure	
 Shopping frequency Length of time shopping at the mobile market (in months) (see Process Follow-up Survey) 	Study participants at follow-up data collection	Descriptive and as described in Aim 1 analysis plan
Contamination and dose— objective (R, A)	Fruit and vegetable purchase data collection	Number of trips to Mobile Market	Study participants at baseline and follow-up data collection	Descriptive and as described in Aim 1 analysis plan
Intervention participant market purchases (R, A, M)	Point of sale system with customer loyalty program (Market Members) to track purchases ^a	
 Frequency of purchases Dollars spent on market purchases Number and types of items purchased (see Mobile Market purchasing protocol) 	Intervention site participants during the implementation period	Descriptive and as described in Aim 2 analysis plan
Key features and suggestions for improvement from intervention participants (A, I)	Open-ended qualitative process survey and interviews about key features that make the market helpful and suggestions for improvement	
 Open-ended responses (see process survey) Qualitative interview transcripts (see qualitative question guide) 	Intervention site participants at follow-up data collection and intervention site participants selected for interviews	See Aim 3

Notes: ^aIntervention site participants will all be enrolled in the Market Member program as part of their participation in the study. All Mobile Market customers, regardless of whether they are at a research site or are participating in the research study, can enroll in this program and receive nominal discounts (\$5 off) every 3-4 shopping trips (see Mobile Market purchasing data collection protocol attachment).

5.3 Randomization: The sites recruited for the trial will be randomized to mobile market service first or the waitlist control (to receive mobile market service after the data collection for each wave is complete). The randomization will be completed by the study statistician who will be blinded to the study site location names. After randomization, the study statistician will be unblinded to site names by being provided access to the key that matches sites with their assigned numbers. This will inform him which sites were randomized to the intervention and waitlist control. The study statistician will then inform the mobile market co-investigator of the sites randomized to the intervention approximately 2 months prior to the end of data collection to allow time for the mobile market to plan for market routes and schedules. Participants, site locations, the PI and other UMN trial investigators and staff will be blinded to (i.e., not be informed of) site randomization results until after baseline data is collected. Of note, only the project manager and the study

statistician will be aware of the key (the link between the site names and the assigned site numbers that will be used in analysis) until analysis is complete.

Intervention/waitlist control: The intervention, Twin Cities Mobile Market service will be provided in the communities recruited for the trial. This service will be the same service provided to other community sites with ongoing Mobile Market service. Service will be available to anyone in the community regardless of trial enrollment. Intervention sites will receive mobile market service following two months of strategic community engagement. Waitlist control sites will receive mobile market service after follow-up data collection for the wave is complete. More detail is provided in IRB protocol section 4.1.

Data analysis: Data will be analyzed by research staff to answer study related research questions and to determine the individuals who are the high and low adopters of mobile market shopping for qualitative interviews related to the study's third aim. See details in IRB protocol section 17.

The following actions will be taken if a participant misses a study visit:

- The study team must attempt to contact the participant and reschedule the missed visit as soon as possible, counsel the participant on the importance of maintaining the assigned visit schedule, and ascertain whether the participant wishes to and/or should continue in the study.
- Before a participant is deemed lost to follow-up, the investigator or designee must make every effort to regain contact with the participant, where possible, by text, email, telephone calls, and if necessary, a certified letter to the participant's last known mailing address. These contact attempts will be documented in the participant's contact log. Should the participant be unreachable for 5 consecutive attempts by phone or text without response/reply followed by a certified letter without response, the participant will be considered to have withdrawn from the study.

5.4 Follow-Up: The data collection process will be identical to that of baseline data collection with a few exceptions, noted below. There is not long-term follow-up data collected.

Quantitative measures of mobile market features. Features of the market that could influence market shopping adoption will also be measured at follow-up data collection for the participants at sites randomized to receive mobile market services first (vs. waitlist service to start after final data collection). These features include perceived convenience of market service (not at all convenient to very convenient); whether the market meets participant cultural food needs (yes/no); perceived affordability of market food prices (not at all affordable to very affordable); and whether they would recommend the market to a friend (yes/no). Customer satisfaction of the market's: (a) location and timing; (b) selection of food items available; (c) prices; (d) customer service; and I overall shopping experience

(not at all satisfied to very satisfied) will also be measured. See process survey attachment.

Qualitative interview questions. Qualitative interviews will be conducted with a subsample of intervention participants who are high and low mobile market adopters after the intervention is complete (see section 11 for specifics of how participants would be selected for the interviews). Interviews will be audio recorded with a digital voice recorder and occur in person or by phone. Main interview questions will inductively explore factors that influenced market shopping and shopping adoption. Interviews will unfold consistent with qualitative methodology and allow the participants to shape the flow and content.¹¹⁰ Probing and clarifying questions will be asked as needed.^{110,111} See qualitative interview guide attachment.

- 5.5 Individually Identifiable Health Information: This research study will collect participants' names, contact information, dietary intake data, fruit and vegetable purchasing data and minimal self-reported health information (i.e. has a doctor ever told you that you have the following conditions or health problems (with yes, no response options): high blood pressure or hypertension, high cholesterol or hyperlipidemia, diabetes, heart disease, depression or anxiety, overweight/obesity.

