13.0 Withdrawal of Participants

13.1 Withdrawal Circumstances: The following are the circumstances under which participants would be withdrawn from the research without their consent:

- If they are lost to follow up
- If they behave inappropriately toward study staff
- If they show signs of diminished capacity to consent

13.2 Withdrawal Procedures: Participants will be informed that if any point they no longer wish to be in the study, they may withdraw from the study. If a participant tells the research staff they would like to withdraw from the study, the research staff will ask for and document reason for withdrawal. Any data provided by the participant will continue to be used in the study, unless they formally request that data is not used. No further data will be collected from a participant who withdraws from the study.

SOCIAL PROTOCOL (HRP-580)

PROTOCOL TITLE: Mobile Food Market Cluster Randomized Trial

VERSION DATE: 1/5/2023

13.3 Termination Procedures: This study may be temporarily suspended or prematurely terminated if there is sufficient reasonable cause (see stopping rules on the DSMP). Written notification, documenting the reason for study suspension or termination, will be provided by the suspending or terminating party to the funding agency and regulatory authorities. If the study is prematurely terminated or suspended, the PI will promptly inform the IRB and will provide the reason(s) for the termination or suspension. The study may resume once concerns about safety, protocol compliance, and/or data quality procedures are addressed and satisfy the funding agency and IRB. If the study is terminated, the study team will notify the participants of the study termination.

Data collected for the study prior to the study termination will be handled in the following manner:

- If the study is terminated due to safety reasons, the data related to AEs will be evaluated.
- If the study is terminated for any other reason, the regulatory and/or institutional document/data retention policies will apply.

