17.0 Statistical Considerations

17.1 Data Analysis Plan: See section 17.3

17.2 Power Analysis:

Power calculation. For the primary outcome of change in HEI scores, power is computed based on a t-test at the individual client level, but the sample size is inflated for the group randomization design by a factor of $1+(m-1)*ICC$ where m is the average cluster size and ICC is the intraclass correlation. In Co-Investigator [name]'s study with participants similar to the proposed study (i.e., from the same communities with similar income and diversity levels), the HEI SD was 11.2.⁹⁰ In our preliminary customer intercept survey study, we found an ICC of 0.0004. Therefore, to be conservative, we assume an SD of 12 and an ICC of 0.01. Under these assumptions with a two-sided type I error rate of 5%, this study will have 80% power to detect a mean difference of 5.5 HEI points between intervention and control participants with an average cluster size m of 20 and number of clusters k of 12 for a total of 264 participants (132 per group). This calculation assumes an attrition rate of 20%. Detection of a 5.0 point difference in HEI is clinically significant, as it corresponds to a lower risk of cardiovascular mortality and lower risk of all-cause mortality.¹²² Additionally, given our conservative approach, we may ultimately be adequately powered to detect even smaller differences in HEI scores between intervention and control sites.

17.3 Statistical Analysis:

Aim 1: The primary analysis will compare the mean within-person, baseline to follow-up change in HEI-2015 between the mobile market and waitlist control groups. Changes in HEI-2015 will be modeled via a Generalized Estimating Equation (GEE) linear model to account for the possible correlation of outcomes within community sites. Food insecurity, as measured by the U.S. Adult Food Security Survey Module, will be analyzed similarly. Baseline characteristics of randomized

SOCIAL PROTOCOL (HRP-580)

PROTOCOL TITLE: Mobile Food Market Cluster Randomized Trial

VERSION DATE: 1/5/2023

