groups will be summarized to assess whether any chance imbalances between groups are scientifically meaningful. If necessary, imbalanced variables will be adjusted for in outcome analyses. For variables with > 10% missing values, we will compare characteristics between individuals with missing and non-missing values and perform multiple imputation if needed.¹²³ Since several hypotheses on different outcomes are of interest, we will focus mainly on reporting confidence intervals rather than null hypothesis significance testing, an approach in line with current recommendations.¹²⁴ If the overall intervention effect is sufficiently large (i.e., of similar clinically meaningful size that we are powered to detect), we will use exploratory analyses to assess the presence and magnitude of possible treatment-covariate interactions, where again the focus will remain on identifying interactions of a clinically meaningful magnitude rather than those that achieve a pre-determined significance threshold. In particular, we will investigate the influence of sex as a biological variable by assessing whether intervention effects vary by sex. While the primary analyses will be conducted within an intent-to-treat (as randomized) framework, we will also perform dose-adjusted analyses to investigate the association between frequency and volume of use of the mobile market and the outcomes of interest, and whether these usage measures mediate the effects of the intervention.¹²⁵ For process and implementation measures taken at the site level, the focus will be mainly on creating meaningful descriptive statistics and visualizations.

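### Sections 5.3 and 13 turn sustained non-contact into withdrawal and stop data collection, so some follow-up outcomes may be lost from people who never withdrew consent

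*Combined protocol and SAP*

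**What the plan says.** Three provisions act together.

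- **Section 5.3, actions after a missed study visit.** Staff try to reschedule, and before loss to follow-up is declared "the investigator or designee must make every effort to regain contact with the participant". The end point is then defined: "Should the participant be unreachable for 5 consecutive attempts by phone or text without response/reply followed by a certified letter without response", in which case "the participant will be considered to have withdrawn from the study".
- **Section 13.1, withdrawal without the participant's consent.** Three grounds are listed. The first is "If they are lost to follow up"; the others are inappropriate behaviour toward staff and signs of diminished capacity to consent.
- **Section 13.2, withdrawal procedures.** Data already given are kept: "Any data provided by the participant will continue to be used in the study, unless they formally request that data is not used". The section ends: "No further data will be collected from a participant who withdraws from the study".

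On the analysis, section 17.3 states: "The primary analysis will compare the mean within-person, baseline to follow-up change in HEI-2015 between the mobile market and waitlist control groups". Section 5.2 places outcome measurement at baseline and once more after six months of market service, and section 5.4 says there is no longer-term follow-up.

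**The concern.** Failing to answer the phone is not withdrawal of consent. Someone who withdraws has told the trial to stop. Someone who cannot be reached has not, and their outcome is still wanted. The protocol gives both the same label, and the label carries a ban on further measurement.

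The change score needs a follow-up value, and there is one occasion to get it. A participant labelled withdrawn before that occasion has no observed primary outcome. Yet the follow-up visit is held at or near the community site, its first recall is in person, and participants live within half a mile. It is a realistic place to meet someone who has stopped answering calls.

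The loss may also be selective. People who are hard to reach may differ from those who are not. Section 4.1 gives intervention participants a monthly contact on top of the retention contacts, so reachability could differ by arm. Section 17.3 offers multiple imputation only where more than 10% of values are missing and if judged necessary, and states no sensitivity analysis for missing outcomes.

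**Working it through.** **1. Does the text produce the result?**

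| Step | Source | Effect |
|---|---|---|
| Five unanswered attempts and an unanswered certified letter | 5.3 | Classed as withdrawn |
| Loss to follow-up | 13.1 | Withdrawn without consent |
| Withdrawn | 13.2, last sentence | No further data |
| Person resurfaces | No provision found | Measurement not provided for |

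No minimum period is set for the five attempts, and no clause allows reinstatement.

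**2. Who could be lost avoidably?**

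- *People who miss the follow-up visit, meet the contact rule, then reappear before the wave's follow-up closes.* This follows directly from the text.
- *People lost during the baseline phone recalls.* Section 5.1 puts about two months of engagement and six of service before follow-up, so they could be closed out long before it. This holds only if a phone recall counts as a study visit. Section 5.2 contrasts the in-person recall at the data collection visit with the two later phone recalls, so this is a possible reading, not a certain one.
- *People who stay unreachable throughout.* They are missing under any rule and are not counted here.
- *People lost after the in-person follow-up recall.* They may still have a partial HEI; the documents state no minimum number of recalls.

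**3. What does missing follow-up cost in power?**

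Inputs: 264 enrolled in 12 sites and 15% attrition (section 11.1); SD 12, ICC 0.01, two-sided 5% (section 17.2).

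Formulas: N = 264 × (1 − attrition); m = N/12; DE = 1 + (m − 1) × 0.01; SE = 12 × √(4 × DE/N); detectable difference at 80% power = (1.96 + 0.84) × SE; power for 5.0 points = Φ(5.0/SE − 1.96).

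The plan's own case first: N = 264 × 0.85 = 224.4; m = 18.7; DE = 1.177; SE = 12 × √(4 × 1.177/224.4) = 1.738; detectable difference 4.87; power Φ(2.877 − 1.96) = 82%. Section 11.1 states 80% for 5.0 points with 224 analysed, so its figure is reproduced.

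| Total attrition (assumed beyond the plan's 15% and 20%) | N | Detectable difference | Power for 5.0 |
|---|---|---|---|
| 15% | 224 | 4.87 | 82% |
| 20% | 211 | 5.00 | 80% |
| 25% | 198 | 5.14 | 78% |
| 30% | 185 | 5.29 | 75% |

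Each further 5 percentage points of loss costs about 2 to 2.5 points of power. The table describes attrition from any cause. The documents contain nothing from which the rule's share could be computed.

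**4. What could selective loss do?**

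Assume that those lost would have had a mean change g points lower than those retained in the same arm, and that the fractions lost are r₁ (intervention) and r₀ (control). The bias in a completers' comparison is g × (r₁ − r₀). With assumed g = 5, r₁ = 0.05 and r₀ = 0.15 it is 5 × (−0.10) = −0.5 HEI points; with g = 3 it is −0.3. With equal loss in both arms and the same g it is zero. None of these inputs comes from the documents. They show only that bias needs loss that is both selective and different between arms, or different in kind between them.

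**The case against.** The strongest reply is that the rule bites late and rarely. It follows a missed study visit and needs five consecutive failures plus a certified letter, on top of the retention contacts in section 12.1, which section 4.1 extends to waitlist participants. Consent and the first recall take place at the baseline visit, and no participant visit is scheduled during the six months of service. The visit most likely to be missed is therefore follow-up itself, and someone unreachable then is mostly missing whatever the protocol says. This stands, and it limits the point to sustained non-contact. A reader might infer that a short silence costs the outcome, or that a missed baseline phone recall necessarily bars the six-month visit. The text does not support the first, and supports the second only on one reading of what a visit is.

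A second reply is that section 13.2 concerns people who tell staff they want to leave. Its earlier sentences do. Its last sentence is not so limited, and section 5.3 uses the same term for unreachable participants. At best the text is ambiguous, and staff could apply it differently across sites or waves.

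A third is that missing outcomes do not breach intent-to-treat. This is right. The plan says "While the primary analyses will be conducted within an intent-to-treat (as randomized) framework", which governs analysis by assigned arm. Collected data are kept, and a missing-data approach is given. A reader might infer a contradiction, but there is none; the rule only leaves more for the missing-data methods to handle.

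**Conclusion.** The point holds as a correctable weakness in follow-up procedure. Read together, sections 5.3, 13.1 and 13.2 class sustained non-contact as withdrawal, stop data collection and provide no way back. Because the primary outcome depends on one follow-up assessment, applying the rule can add missing outcomes and cannot prevent any.

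Its size is unknown. A reader might take the fall from 82% to 75% power as the effect of this rule. It is not: it is the arithmetic of total attrition between 15% and 30%, of which 15% (section 11.1) or 20% (section 17.2) is already allowed for, and power for 5.0 points is still 80% at 20% loss. Nor do the documents show that the loss would be non-random; that is plausible, not established. The case rests on avoidability and low cost, not on power.

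It assumes that the last sentence of section 13.2 applies to everyone classed as withdrawn, and that some unreachable participants could be found before follow-up closes. It is a cheap improvement.

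**What to change.** Amend sections 5.3, 13.1 and 13.2 together:

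1. In 5.3, record the outcome of the contact procedure as unable to contact, with a missed assessment, rather than as withdrawal. Remove loss to follow-up from the list in 13.1.
2. Keep these participants eligible for follow-up data collection, and approach them at it, until the wave's window closes. State when that is, or refer to the attached procedure if it already does. It should fall before market service starts at the waitlist sites.
3. Limit the bar on further data in 13.2 to participants who ask to withdraw, or who are withdrawn under the other two grounds in 13.1 (inappropriate behaviour, diminished capacity). Leave both grounds as they are.
4. Continue extracting loyalty-card purchases for uncontactable intervention participants only if the signed consent permits it. The consent form is not among the documents reviewed, so this must be checked first. These data serve the adoption and dose analyses, not the primary comparison.

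The cost is a protocol wording amendment and a few extra contact attempts at visits already scheduled. People who ask to leave are protected exactly as now.
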